6.2.4 Observational Period

During the Observation Period, collection of the following information may be completed during a clinic visit, telephone contact, or search of a public access source (for date of death):

- Vital status
- Study medication related AEs, see section 5.2.2.2
- Anti-cancer therapy, including radiotherapy << *disease specific details* >>

The method of contact and the date of contact will be recorded in the (e)CRF.

7. STATISTICAL METHODS AND DETERMINATION OF SAMPLE SIZE

7.1 Statistical design-model

Given the poor prognosis of this patient population and data from other studies of salvage therapy, a PFS6 of $\geq 20\%$ is considered to be important for this regimen, while a PFS6 $< 5\%$ will be considered to be of poor interest. A two-stage minimax design will be used which will enroll a maximum of 27 subjects: 13 during stage 1 and 14 during stage 2. If no patients are free from progression at 6 months among 13 patients during the first stage, then the trial ends with the conclusion that this drug is not worth further study. Otherwise the trial proceeds to the second stage. Since some (5-10%) accrued patients may not be evaluable, up to 29 patients will be enrolled.

7.2 Null and alternative hypotheses

The null hypothesis for this study is that PFS at 6 months will occur in less than 5% after treating with Gilotrif whereas the study alternative hypothesis is that PFS at 6 months will be observed in 20% or more of all patients, which will signify important activity of Gilotrif in this patient population.

7.3 Planned analyses

This trial will be conducted with Intention-To-Treat and all patients for whom PFS6 is evaluable and can be calculated will be included in the final analysis for estimating progression free survival. Statistical significance will be defined as a p-value < 0.05 .

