1.1.3 Current systemic chemotherapy for advanced PSCC

High level evidence for the value of systemic therapy does not exist in this orphan disease. The efficacy of adjuvant therapy is unproven. In patients with bulky primary disease or fixed or bulky inguinal or pelvic lymph nodes (LN), multimodality therapy including neoadjuvant chemotherapy followed by surgery and node resection is offered (58-61). Generally, cisplatin-based combinations employed in the pre-and post-taxane era have demonstrated similar response-rates (25-50%) and survival. Hence, a single optimal neoadjuvant systemic regimen has not been established and the value of surgery following chemotherapy for those with LN involvement remains unproven.

Systemic chemotherapy alone is offered for men with distant metastases and clinical trials are strongly encouraged given the poor efficacy of currently available regimens. A variety of first-line cisplatin-based, systemic therapy regimens have been reported in mostly small single institution retrospective and phase II studies, as the rarity of this disease prohibits the conduct of large randomized trials (58, 59, 62-74). Older trials employed bleomycin and methotrexate as partners, while newer studies have investigated taxanes, 5-fluorouracil and gemcitabine combinations with median survivals ranging from 6 to 11 months. Historical data with combination BMP demonstrated a median survival of only 28 weeks (68, 75, 76). In the largest prospective study of this regimen, there were 5 complete and 8 partial responses in 40 evaluable patients for a 32.5% response rate (76). Unfortunately, in this study, 5 treatment related deaths occurred and 6 other patients had 1 or more life threatening toxic episodes. Hence, the toxicities of bleomycin-containing regimens have been recognized and considered to be prohibitive. However, outcomes with non-cisplatin based regimens are unclear. A recent study by our group evaluated prognostic factors in 140 patients receiving first-line chemotherapy and identified performance status and metastatic sites as major prognostic factors (77).

Second-line therapy is also not established, and taxanes have been used with marginal activity (78). In a prospective, multicenter phase II trial, 25 patients were enrolled and treated with paclitaxel 175 mg/m² every 3 weeks. Partial responses were observed in 20%. The median PFS was only 11 weeks, and the median OS was 23 weeks.

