2. RATIONALE, OBJECTIVES, AND BENEFIT - RISK ASSESSMENT

2.1 Rationale for performing the trial evaluating Gilotrif as salvage therapy for advanced PSCC

Gilotrif is a highly promising irreversible pan-EGFR inhibitor, which was recently approved for non-small cell lung cancer with EGFR mutations (97). Median PFS was 11.1 months for Gilotrif and 6.9 months for chemotherapy with cisplatin plus pemetrexed in a phase III trial (hazard ratio [HR], 0.58; 95% CI, 0.43 to 0.78; $P = .001$). Median PFS among those with exon 19 deletions and L858R EGFR mutations ($n = 308$) was 13.6 months for Gilotrif and 6.9 months for chemotherapy (HR, 0.47; 95% CI, 0.34 to 0.65; $P = .001$). The most common treatment-related adverse events were diarrhea, rash/acne, and stomatitis for Gilotrif and nausea, fatigue, and decreased appetite for chemotherapy. Given the tumor tissue studies providing robust supportive evidence for the expression of the EGFR family of proteins, a strong rationale may be made for investigating the role of Gilotrif as salvage therapy for advanced PSCC. Indeed, another phase II trial is evaluating dacotinib, another pan-Her inhibitor as salvage therapy for PSCC (NCT01728233). Moreover, PSCC is an orphan malignancy and a strong rationale can be made for the approval of agents by regulatory agencies based on robust activity in phase II trials.

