3. DESCRIPTION OF DESIGN AND STUDY POPULATION

3.1 Overall study design and plan

[figure not shown]
This is a non-randomized 2-center phase II trial (overall N=29, evaluable N= 27) to evaluate Gilotrif 40 mg po qd for patients with locally advanced unresectable or metastatic progressive PSCC following prior chemotherapy. UAB is the coordinating institution and the other participating institution is the University of Southern California (USC). Patients will undergo clinical examination every 4 weeks and radiographic work-up at baseline and then every 8 weeks. Patients will continue therapy until progression or intolerable toxicities. Patients removed from therapy for reasons other than progression will be followed to identify progression or until initiation of other therapy. Twenty archival formalin-fixed paraffin embedded (FFPE) tissue slides per patient will be acquired for future analyses including histologic sub-type, IHC for EGFR, Her2, Her3, Her4, gene expression by nanostring for a panel of kinase and cancer associated genes and Human Papilloma Virus status by PCR (polymerase chain reaction) for HPV-DNA.

The eligible population of patients includes men with pathologically proven locally advanced or metastatic (lymph node or distant metastasis i.e. N+ or M1) PSCC which has received ≥ 1 systemic chemotherapy regimens within last 6 months with ECOG PS 0-2 & optimal organ function (Hb>8.5, ANC>1500/mm³, Platelet count>100K, Total bilirubin <1.5 of ULN, creatinine clearance >45ml/min, ALT and AST<2.5X ULN, for patients with liver involvement ALT and ALT<5X ULN). The disease should be measurable by RECIST 1.1 criteria. Gilotrif will be administered orally 40mg daily continuously. Continuous administration of 4 weeks is considered one cycle. Therapy will continue until progression (by RECIST 1.1) or severe toxicities. Patients removed from the trial for toxicities or other reasons will continue to be followed until progression or starting a new agent. Complete Blood Count (CBC) & Comprehensive metabolic panel (CMP) evaluations will be done performed on day 1 every 4 weeks. CT chest, abdomen and pelvis will be performed every 2 cycles (8 weeks). A bone scan will be performed only if bone pain or high alkaline phosphatase are observed. An evaluable patient is defined as any patient who qualifies for the trial and receives at least one dose of study drug.

Progression of disease will be defined clinically as the first occurrence of any of the following:

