3.3 Selection of study populationGeneral Guidelines

Eligible patients will be entered on study centrally at the Kirklin Clinic, UAB Hospitals, and USC (research nurse to be designated by [name] Director of Oncology Clinical Trials, CSU, UAB). All sites should call the Study Monitor at UAB to verify agent availability. Following registration, patients should begin protocol treatment within 72 hours. Issues that would cause treatment delays should be discussed with the Principal Investigator. If a patient does not receive protocol therapy following registration, the patient's registration on the study may be cancelled. The Study Monitor should be notified of cancellations as soon as possible.

Registration Process

The Clinical Trials Network Monitoring Office (CTNMO) of the UAB Comprehensive Cancer Center (CCC) coordinates investigator-initiated clinical trials under Good Clinical Practice conditions at participating sites to achieve timely study subject enrolment. Once a study subject has been screened and deemed eligible for study entry by the participating site, a study-specific study subject eligibility checklist, a copy of the dated and signed consent form, and corresponding source documentation are faxed to the participating site study coordinator for eligibility verification. Subsequently, a study-specific number is assigned to the study subject and sent to the participating site. Finally, a Patient Registration Form is completed and faxed by the CTNMO site to the participating study coordinator. Queries regarding data accuracy are forwarded from the CTNMO to the participating site coordinator for clarification or correction. Once the participating site addresses queries, any corrected data forms or copies of corrected source documentation are faxed to the CTNMO.

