5.4 Appropriateness of measurements

The RECIST criteria 1.1 (section 10.4) (100) to be used for evaluation of tumour response are well established and scientifically accepted. The US NCI CTCAE criteria Version 3.0 (or 4.0) are used in the assessment of adverse events in cancer patients.

6. INVESTIGATIONAL PLAN**6.1 Visit schedule****6.1.1 Treatment period**

In case a patient misses the scheduled study visit but reports to the investigative site before the next scheduled study visit, the missed visit will be performed. The current date and reason for the delayed visit will be noted in the source documentation. All subsequent study

visits should take place at the start of the next treatment cycle per the flow chart. In the event of any study drug interruption or delay of treatment, the tumour assessment scheduled will not be changed.

6.1.2 End-of-Treatment and Follow-up period.

In the case study medication is permanently discontinued due to reasons other than disease progression, withdrawal of consent, or ability to access Gilotrif outside of the protocol, patients will be followed up for tumour response until disease progression. Follow up will be every *1 month* to document the date of disease progression. Tumor assessment data collection will be discontinued upon progression of the tumour and/or the patient commences other anti-cancer treatment. The investigator will maintain contact every *3 months*, whether by telephone or out-patient attendance, with the patient or the patient's family.

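### The PFS6 estimate is labelled Intention-To-Treat but drops patients whose 6-month outcome is unknown, and no missing-data rule covers them; this affects the estimate, not the go/no-go decision

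*Combined protocol and SAP*

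**What the plan says.** Section 7.3 states that the trial follows Intention-To-Treat and, in the same sentence, that "all patients for whom PFS6 is evaluable and can be calculated will be included in the final analysis for estimating progression free survival".

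Other sections describe the analysed patients differently:

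- **3.1:** "An evaluable patient is defined as any patient who qualifies for the trial and receives at least one dose of study drug". Nothing here depends on the outcome being known.
- **7.2:** the 20% alternative is framed over all patients.
- **7.3.1:** the drug is of interest if at least 4 of the total of 27 are progression-free at 6 months, with a window of two weeks either side for scans.
- **7.3.3:** the stage 1 look takes place once PFS6 has been calculated for the 13 recruited patients.
- **7.4:** one general sentence on data integrity. It does not say whether unknown status is a failure, censored, excluded or replaced.

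Kaplan-Meier is specified for overall survival only (7.3.2).

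On follow-up, 3.1 says "Patients removed from the trial for toxicities or other reasons will continue to be followed until progression or starting a new agent". Section 6.1.2 provides monthly progression follow-up when drug is stopped for "reasons other than disease progression, withdrawal of consent, or ability to access Gilotrif outside of the protocol", and adds: "Tumor assessment data collection will be discontinued upon progression of the tumour and/or the patient commences other anti-cancer treatment".

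**The concern.** Whether PFS6 can be calculated is settled after treatment starts and may be related to how the patient is doing. Selecting on it is not Intention-To-Treat, and it is not the one-dose set of 3.1 either. If 7.3 means the 3.1 definition when it says evaluable, its second condition still filters on outcome availability.

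Unknown status is foreseeable. Withdrawal is a listed reason for removal (3.3.4). Section 6.1.2 exempts withdrawal and drug access outside the protocol from progression follow-up, and ends tumour data collection at new anti-cancer treatment. Section 3.1 has no such exemptions for withdrawal or outside access, so the two sections differ on who is followed. Progression in 3.1 means RECIST progression or death, so a patient who starts another agent before either has no assigned 6-month status.

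What is at stake is the primary estimate, in an unblinded single-arm trial where the analysis set could be settled after outcomes are seen. The stage 1 rule also has no defined reading if one of the 13 cannot be calculated.

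**Working it through.** **Inputs.** Null 5% and alternative 20% (7.2); 13 then 14 patients, stopping at 0 of 13 (7.1, 7.3.3); success at 4 or more of 27 (7.3.1); one-sided 5% level and 80.1% power (7.5). The share with unknown PFS6, *d*, is not in the documents. I assume 5% and 10%, which is 1.35 and 2.7 of 27 patients.

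**1. The plan's own figure.** P(success | p) = Σ over x₁ = 1 to 13 of P(Bin(13, p) = x₁) × P(Bin(14, p) ≥ 4 − x₁).

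- p = 0.20: 0.8011, which reproduces the stated 80.1%.
- p = 0.05: 0.0416, within the 5% limit.

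**2. Does dropping patients change the decision?** The count of progression-free patients cannot rise when patients are removed. The remaining question is whether 4 is still the right threshold for a smaller denominator. Exact one-sided tails at 5%:

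| Denominator n | Tail probability | Reading |
|---|---|---|
| 16 | P(X ≥ 3) = 0.0429 | 3 would suffice |
| 17 | P(X ≥ 3) = 0.0503 | 4 needed |
| 28 | P(X ≥ 4) = 0.0491 | 4 suffices |
| 29 | P(X ≥ 4) = 0.0548 | 5 needed |

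The critical count is 4 for every n from 17 to 28. Leaving out up to 27 − 17 = 10 patients does not move it.

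**3. Does it change the estimate?** Let p be the true rate in all treated patients and s the rate among the unknown. The calculable subset estimates (p − d·s)/(1 − d). With p = 0.20:

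| Unknown patients | d = 5% | d = 10% |
|---|---|---|
| All would have failed (s = 0) | 0.20/0.95 = 21.1% | 0.20/0.90 = 22.2% |
| Half the success rate (s = 0.10) | 0.195/0.95 = 20.5% | 0.19/0.90 = 21.1% |
| Same success rate (s = 0.20) | 20.0% | 20.0% |

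**4. A result on the threshold (Clopper-Pearson 95% intervals).**

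- 4/27 = 14.8% (4.2 to 33.7), as in the table in 7.3.2.
- 4/25 = 16.0% (4.5 to 36.1).
- 4/24 = 16.7% (4.7 to 37.4).

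**5. Counting unknown as not progression-free.** If 5% and 20% are rates in all patients, as 7.2 words the alternative, step 1 applies unchanged. If they are rates among patients of known status and unknown status is unrelated to outcome, each rate is multiplied by (1 − d):

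- d = 5%: rates 0.0475 and 0.19, giving alpha 3.5% and power 76.5%.
- d = 10%: rates 0.045 and 0.18, giving alpha 3.0% and power 72.4%.

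**The case against.** The plan works to keep unknowns few. Section 6.1.2 requires monthly follow-up for progression after most non-progression discontinuations, including toxicity. Section 6.1.1 keeps the tumour-assessment schedule fixed through drug interruptions. Section 6.2.3 adds a CT about 28 days after the last dose whatever the reason for stopping, and 6.1.3 adds vital-status contacts and a sweep. The success rule is tied to 27 patients. At an assumed 10% unknown the estimate moves by at most 2.2 points, while the exact interval at 4/27 is 29.5 points wide.

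All of this stands, and it limits the size of the point. It does not supply the missing rule: patients who withdraw, obtain the drug elsewhere or start another treatment can still have unknown status, and 7.3 as written removes them.

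Several stronger readings are tempting, and the documents do not support them:

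- **The false-positive rate is inflated.** Exclusion adds no successes, and the threshold of 4 holds from 17 to 28 patients.
- **Incalculable patients are replaced within the cap of 29.** The plan does not say so. Section 3.3 allows cancellation "If a patient does not receive protocol therapy following registration", so the two extra places can be read as cover for undosed or ineligible patients.
- **The estimate must be too high.** That requires the omitted patients to do worse than the rest, which the documents do not establish.
- **A scan just outside the two-week window leaves status unknown.** A clean scan after the window still shows that the patient was progression-free at 6 months.
- **The approval argument rests on this estimate.** Section 2.1 says "a strong rationale can be made for the approval of agents by regulatory agencies based on robust activity in phase II trials", which refers to phase II activity in general and does not mention PFS6.

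**Conclusion.** The point holds as a conflict over the analysis set combined with a missing rule for the primary endpoint. Section 7.3 lets an event after treatment start decide who enters the PFS6 estimate, contrary to its own label, to the one-dose definition in 3.1, and to the patients counted in 7.2 and 7.3.1.

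The go/no-go conclusion and the design's operating characteristics (alpha 4.2%, power 80.1%) are sound. The effect on the estimate is modest: from a true 20%, up to 21.1% or 22.2% at an assumed 5% or 10% unknown, and no upward bias if unknown patients share the prognosis of the rest. Those upper values need every unknown patient to have been a failure. The documents give neither the number of unknowns nor their prognosis, so actual size and direction are open. It should be fixed because it concerns the primary endpoint and the remedy is simple.

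**What to change.** - **7.3, 7.3.1 and 7.3.3:** define the primary set as the first 27 eligible patients who received at least one dose (the first 13 for stage 1), with no replacement for unknown PFS6. Call it the eligible treated population. It omits undosed and ineligible patients, so the Intention-To-Treat label should go.
- **7.4:** count any patient not documented progression-free at 6 months as not progression-free, and state that a later clean scan is documentation.
- **Sensitivity analyses:** report PFS6 in the calculable subset and a Kaplan-Meier PFS6.
- **3.1 and 6.1.2:** reconcile who is exempt from progression follow-up.

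The cost is protocol and SAP wording only. Alpha and power stay at 4.2% and 80.1% if the design rates refer to all patients. The downside is a conservative estimate. If the rates refer only to patients of known status, alpha and power fall to 3.5% and 76.5% at 5% unknown, and to 3.0% and 72.4% at 10%.

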7.3.1 Primary analyses

The primary endpoint of this study is the rate of progression free survival (PFS) at 6 months with a window of plus or minus two weeks to give leeway for CT scans to be performed (PFS6). If four or more of the total 27 patients remain progression free at 6 months, this drug will be considered to be of significant interest.

7.3.2 Secondary analyses

The secondary endpoints are not formally powered for, but will be examined in the evaluable population. RECIST responses, regression and toxicities will be analyzed as secondary endpoints. Descriptive statistics including frequencies and proportions will be calculated to summarize safety and toxicity outcomes. Specifically, the number of adverse events (AE) and serious adverse events (SAE) will be tabulated and summarized. Point estimates and two-sided, exact binomial (Clopper-Pearson) 95% confidence intervals (CI) will be calculated to estimate the incidence of AEs and SAEs. The precision of these estimates, i.e., width of the confidence interval, will depend on the estimated incidence of each outcome. The table below gives the exact 95% confidence intervals for a range of incidences, assuming 27 evaluable subjects.

Number of subjects experiencing event	Estimated Incidence	95% Exact CI for Incidence		Width of CI
		Lower Limit	Upper Limit	
1	0.037	0.001	0.190	0.189
2	0.074	0.009	0.243	0.234
4	0.148	0.042	0.337	0.295
7	0.259	0.111	0.463	0.352

14	0.519	0.319	0.713	0.394
----	-------	-------	-------	-------

The Kaplan-Meier method will be used to estimate OS rates over time with standard errors estimated using Greenwood's formula. Chi-square or Fisher's exact test will be employed to determine bivariate association of biomarker status with PFS6 and objective response.

NanoString technology will be applied to measure the expression of candidate cancer and kinase genes that may predict outcomes and benefit from Gilotrif, and six internal reference genes (101). The nSolver text files (.csv) and NanoString .rcc files will be imported into Partek Genomic Suite 6.6 (PGS, Saint Louis, MO) for statistics and bioinformatics analysis. The differential expressions are determined by ANOVA. A gene list is then created after false discovery rate (FDR) p value correction by Benjamini and Hochberg method (102). Further functional analysis including gene-gene interactions and signaling pathways will be conducted by using Ingenuity Pathway Analysis (IPA, Redwood City, CA). Due to small study numbers, exact logistic regression models will be used to explore whether tumor biomarker (EGFR, Her2, Her3, Her4, nanostring gene expression) expression predicts for response and freedom from progression. Prognostic impact of gene expression, HPV status and IHC studies will be performed using Cox proportional hazards regression. Variables of interest will be evaluated after adjusting for performance status and presence of visceral metastases. Impact of statistically significant variables will be described using hazard ratios, 95% confidence intervals, and concordance statistics. These results are hypothesis-generating and will require external validation.

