The UAB Comprehensive Cancer Center Data and Safety Monitoring Plan (DSMP) instituted by the CTNMO will monitor subjects treated at UAB and the other 2 institutions participating in the trial. The Clinical Trials Monitoring Committee (CTMC) on a weekly basis will closely monitor adverse reactions observed during treatment. The CTMC is responsible for data and safety monitoring of the trial and adherence to the DSMP. The office of CTNMO will also report any SAE at participating sites outside UAB to the CTMC. The independent Quality Assurance Committee (QAC) is responsible for oversight of the operation of CTMC, including adherence to the DSMP. Reports from the CTMC are reviewed monthly by the QAC.

Protocol Management and Oversight of Participating Site

[name] functions as the sponsor of the trial at UAB and at the participating sites. The participating sites will utilize their respective IRB of record. The Lead Investigator at participating site(s) will be responsible for ensuring that all the required data will be collected and entered onto the Case Report Forms. A teleconference between UAB CTNMO and participating sites every 3 months will ensure discussion of AEs seen across all sites. UAB PI, CTNMO manager and participating site Lead Investigators will discuss management of AEs, and impact of AEs on trial conduct. The CTNMO office will report the outcome of these discussions at CTMC meeting every month. Periodically, monitoring visits will be conducted by CTNMO manager and the participating site Lead Investigator will provide access to his/her original records to permit verification of proper data entry. At the completion of the study, all case report forms will be reviewed by the CTNMO manager and will require his/her final signature to verify the accuracy of the data.

Table 5.2.2.2:1 AE/SAE reporting requirements

Time period	Reporting requirements
From signing of informed consent to ≤28 days after last trial drug administration	Report all AEs and SAEs regardless of relatedness or whether the trial drug was administered. This includes all deaths.
Post-treatment (>28 days after last trial drug administration)	Report only SAEs which are considered related to trial treatment or trial design. Death should be reported as an SAE only when considered related to trial treatment or trial design (because death is an endpoint and will be followed-up separately).

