7.5 Determination of sample size

SAS version 9.3 was used to calculate power and determine sample size. The justification for the proposed sample size is based on applying an exact test for a binomial proportion to Simon's two-stage minimax design(103). A one-sided significance level of 5% was used. Under this design, we will have approximately 80% power (80.1%) to reject the null hypothesis that $PFS < 5\%$ in favour of $PFS6 \geq 20\%$.

A total of up to 29 patients will be enrolled including 27 evaluable patients for this trial. Accrual period will be ~12 months. Follow-up will be at least 6 months after the last patient starts therapy. Thus, the overall duration of the trial is expected to be ~18 months.

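### Toxicity is analysed in a set defined partly by eligibility, so a dosed patient later found ineligible may be left out of the AE and SAE incidence tables

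*Combined protocol and SAP*

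**What the plan says.** All references are to the combined protocol and SAP.

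- **Analysis set.** Section 7.3.2: "The secondary endpoints are not formally powered for, but will be examined in the evaluable population".
- **Toxicity is one of these endpoints.** Section 7.3.2: "RECIST responses, regression and toxicities will be analyzed as secondary endpoints". Section 2.2.2 also lists toxicities as a secondary objective.
- **Definition of evaluable.** Section 3.1: "An evaluable patient is defined as any patient who qualifies for the trial and receives at least one dose of study drug". There is no other definition, and no safety or all-treated set is defined.
- **Planned safety estimates.** Section 7.3.2: "Point estimates and two-sided, exact binomial (Clopper-Pearson) 95% confidence intervals (CI) will be calculated to estimate the incidence of AEs and SAEs". The precision table that follows is introduced by: "The table below gives the exact 95% confidence intervals for a range of incidences, assuming 27 evaluable subjects".
- **Allowance for non-evaluable patients.** Section 7.1: "Since some (5-10%) accrued patients may not be evaluable, up to 29 patients will be enrolled".
- **Data collection is wider than the analysis set.** Table 5.2.2.2:1, for the period from consent to 28 days after the last dose: "Report all AEs and SAEs regardless of relatedness or whether the trial drug was administered".

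**The concern.** A safety summary normally follows exposure: whoever took the drug is counted. Here the set used for toxicity adds an eligibility condition, so exposure alone is not enough to be counted. Section 5.2.2.2 defines on-treatment events by the dates of drug administration, so collection follows exposure while the analysis set need not.

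Two things are at stake. In a trial of at most 29 patients, one man can decide whether an uncommon serious reaction appears in the incidence table at all. And because the plan does not say when or by whom a patient is judged to qualify, the denominator could be settled after the toxicities have been seen. The protocol argues in section 2.1 that phase II results in this rare disease might support regulatory approval, so the safety denominator should be fixed in advance.

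**Working it through.** **1. Reproduce the plan's table.** For x events in n patients, the Clopper-Pearson 95% limits are the 0.025 quantile of Beta(x, n − x + 1) and the 0.975 quantile of Beta(x + 1, n − x). With n = 27:

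| x | Rate | Lower | Upper |
|---|---|---|---|
| 1 | 0.037 | 0.001 | 0.190 |
| 2 | 0.074 | 0.009 | 0.243 |
| 4 | 0.148 | 0.042 | 0.337 |
| 7 | 0.259 | 0.111 | 0.463 |
| 14 | 0.519 | 0.319 | 0.713 |

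All five rows agree with section 7.3.2 to three decimals. The arithmetic is sound; the question is only who is counted.

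**2. Follow the definitions.** Toxicity is a secondary endpoint, secondary endpoints use the evaluable population, and evaluable means qualifies *and* dosed. A patient who is dosed but does not qualify is therefore not evaluable. The Intention-To-Treat sentence in section 7.3 does not rescue him, because what it goes on to specify is the set for estimating progression-free survival.

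**3. Can the case arise?** Inclusion criterion 1 (section 3.3.2) requires confirmed PSCC. Section 6.2.1 obtains the archival specimen for central review in patients already determined eligible, and section 3.3 expects treatment within 72 hours of registration. The schedule in section 3.2 places slide collection in the screening column, but nothing states when the review result must be available. A review that fails to confirm PSCC could therefore arrive after dosing.

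**4. How many patients?** The documents do not say. With 29 enrolled and 27 evaluable, 29 − 27 = 2 patients (2/29 = 6.9%) fall outside the set. Some or all of them may never have been dosed. I therefore assume 0 to 2 dosed but ineligible patients.

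**5. Size and direction.** Suppose x of 27 evaluable patients have the event, and m dosed patients are excluded, k of them with the event. The rate by exposure minus the rate as written is

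(x + k)/(27 + m) − x/27 = [m/(27 + m)] × (k/m − x/27).

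The weight m/(27 + m) is 1/28 = 3.6% for m = 1 and 2/29 = 6.9% for m = 2, so no rate can shift by more than 6.9 percentage points. The sign depends on whether the event rate among those excluded is above or below that among those kept.

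| Assumed case | As written (95% CI) | By exposure (95% CI) |
|---|---|---|
| m = 0 | unchanged | unchanged |
| m = 1, k = 1, x = 0 | 0/27 = 0% (0 to 12.8%) | 1/28 = 3.6% (0.1 to 18.3%) |
| m = 2, k = 2, x = 0 (worst case) | 0/27 = 0% (0 to 12.8%) | 2/29 = 6.9% (0.8 to 22.8%) |
| m = 2, k = 2, x = 2 | 2/27 = 7.4% (0.9 to 24.3%) | 4/29 = 13.8% (3.9 to 31.7%) |
| m = 2, k = 2, x = 7 | 7/27 = 25.9% (11.1 to 46.3%) | 9/29 = 31.0% (15.3 to 50.8%) |
| m = 2, k = 0, x = 4 | 4/27 = 14.8% (4.2 to 33.7%) | 4/29 = 13.8% (3.9 to 31.7%) |

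In the last row the excluded patients had no event, and the rate as written is the higher of the two.

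**The case against.** The strongest reply concerns the word *qualifies*. Section 3.3 has eligibility verified from a checklist and source documents before a study number is assigned. A patient who qualifies may simply be one who passed that step. On that reading, evaluable means registered and dosed, which is already an exposure set. No section describes re-judging eligibility after dosing, and the removal list in section 3.3.4 has no entry for it. This reading is reasonable and lowers confidence in the point. It does not dispose of it, because section 3.1 does not tie the word to registration.

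Other replies stand as limits:

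- The 27 in the precision table is an assumption made to illustrate interval width. It does not fix the denominator.
- The toxicity analysis is descriptive, and the efficacy decision does not use it.
- The allowance above 27 also covers men who never take the drug (section 3.3 foresees cancelled registrations), and they belong in no exposure set.

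A reader might also infer three stronger things that the documents do not support:

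- **A serious or fatal reaction would be lost from the trial's safety record.** All events from consent are reported, deaths on study need both routine and expedited reports, and the monitoring committee reviews adverse reactions weekly (section 5.2.2.2). The stopping rule on toxicity deaths in section 3.3.5 is not confined to evaluable patients. Only the incidence tables and their intervals are affected.
- **AE rates are necessarily biased downward because those excluded are at higher risk.** Several criteria, such as slide availability, measurable disease and timing of the prior regimen, have no evident link to toxicity. Step 5 shows that the shift can go either way.
- **A man with unrecognised interstitial lung disease would be excluded.** Section 3.3.3 bars only known pre-existing disease, so he would not breach that criterion and would stay in.

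**Conclusion.** The point holds as a defect in how the safety analysis set is defined. Taken literally, sections 3.1 and 7.3.2 together can leave a dosed patient out of the AE and SAE incidences if he is later found ineligible. Taken the other way, they do not. The plan does not choose between the two readings.

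Under the assumption of 0 to 2 such patients among 29, the effect lies between nothing and 0/27 against 2/29. That upper end is a constructed worst case: both extra patients dosed, both ineligible, both with the same event, and none among the other 27. The documents give no basis for treating it as likely. Severity is minor to moderate. It does not have to be resolved before the trial can be interpreted, since the underlying events are captured in any case and the primary analysis does not depend on it.

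**What to change.** Add one sentence to section 7.3.2, along these lines: *Toxicities are summarised in all patients who took any Gilotrif, whether or not they are later found to qualify; the number of such patients (up to 29) is the denominator for the exact intervals.* Keep the evaluable population for response. A footnote to the precision table saying that n may reach 29 is optional.

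With this sentence, the meaning of *qualifies* no longer matters for safety, and the denominator is fixed before toxicities are known. The cost is one sentence of analysis text. The data are already collected under section 5.2.2.2, and the sample size, the efficacy analysis and patient management do not change.
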